16.3. Missing Date Information for Prior or Concomitant Medications

For prior or concomitant medications, incomplete (i.e., partially missing) start date and/or stop date will be imputed. When the start date and the stop date are both incomplete for a patient, impute the start date first.

16.3.1. Incomplete Start Date

The following rules will be applied to impute the missing numerical fields. If the stop date is complete and the imputed start date is after the stop date, then the start date will be imputed using the stop date.

Missing day and month

- If the year of the incomplete start date is the same as the year of the date of the first dose of double-blind study drug, then the day and month of the date of the first dose will be assigned to the missing fields.
- If the year of the incomplete start date is prior to the year of the date of the first dose of double-blind study drug, then December 31 will be assigned to the missing fields.

Missing month only

- The day will be treated as missing and both month and day will be replaced according to the above procedure.

Missing day only

- If the month and year of the incomplete start date are the same as the month and year of the date of the first dose of double-blind study drug, then the day of the date of the first dose will be assigned to the missing day.
- If either the year is before the year of the date of the first dose of double-blind study drug or if both years are the same but the month is before the month of the date of the first dose of double-blind study drug, then the last day of the month will be assigned to the missing day.
- If either the year is after the year of the date of the first dose of double-blind study drug or if both years are the same but the month is after the month of the date of the first

dose of double-blind study drug, then the first day of the month will be assigned to the missing day.

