5.2. Protocol Deviations

Major protocol deviations will be identified and documented based on review of protocol deviations before database lock, and will be used to define the PD Evaluable Population (if applicable). The categories of major protocol deviations to be reviewed include, but are not limited to, participants who:

- Did not meet key inclusion/exclusion criteria in the judgment of the evaluability committee
- Received disallowed concomitant medication that could meaningfully impact results
- Had overall treatment compliance rate <80% or >120%

The number and percentage of participants with major protocol deviations will be summarized for the Safety Population by type of deviation. All protocol deviations will be presented in a data listing.

6. Demographics and Baseline Characteristics

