7.1. Prior and Concomitant Medications

All medications that the participant is receiving at the time of Screening until the Follow-up Visit will be collected on the case report form (CRF). All medications will be coded according to the World Health Organization drug dictionary (WHODRUG 2019 Mar).

Prior medication will be defined as any medication with the start date prior to the date of the first dose of the investigational product. Concomitant medication will be defined as any medication with a start date prior to the date of the first dose of study drug and continuing after the first dose of study drug or with a start date between the dates of the first dose of study drug and the follow up visit date, inclusive. Incomplete medication dates will be imputed as described in Section 16.3.

Prior and concomitant medication use will be summarized for the Safety Population by the number and percentage of participants receiving each medication within each therapeutic class. Multiple medications used by a participant in the same category (based on Anatomical-Therapeutic-Chemical classification) will be counted only once. All prior and concomitant medications will be presented in a listing for participants in the Safety population.

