16.3.2. Incomplete Stop Date

The following rules will be applied to impute the missing numerical fields. If the date of the last dose of double-blind study drug is missing, replace it with the last diary call date. If the imputed stop date is before the start date (imputed or non-imputed start date), then the imputed stop date will be equal to the start date.

Missing day and month

- If the year of the incomplete stop date is prior to the year of the date of the last dose of double-blind study drug, then December 31 will be assigned to the missing fields.

Missing month only

- The day will be treated as missing and both month and day will be replaced according to the above procedure.

Missing day only

- If either the year is before the year of the date of the last dose of double-blind study drug or if both years are the same but the month is before the month of the date of the last dose of double-blind study drug, then the last day of the month will be assigned to the missing day.

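### A medicine with a year-only start and a recorded stop month before dosing is classed as concomitant, not prior, because the SAP's start-date check ignores partial stop dates

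*SAP*

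**What the plan says.** SAP 7.1 sends incomplete medication dates to SAP 16.3 and classifies on the result. "Prior medication will be defined as any medication with the start date prior to the date of the first dose of the investigational product". A medicine is concomitant if it began before first dose and continued past it, or if its start lies anywhere from first dose to follow-up, with Day 1 included.

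The imputation rules run in this order:

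- **Sequence (SAP 16.3).** "When the start date and the stop date are both incomplete for a patient, impute the start date first".
- **Start (SAP 16.3.1).** If only the year is known and it is the first-dose year, "then the day and month of the date of the first dose will be assigned to the missing fields".
- **Check on the start (SAP 16.3.1).** The start is replaced by the stop under one condition: "If the stop date is complete and the imputed start date is after the stop date".
- **Stop (SAP 16.3.2).** If the day is missing and the month is before the last-dose month, "then the last day of the month will be assigned to the missing day".
- **Conflict (SAP 16.3.2).** The condition opens "If the imputed stop date is before the start date (imputed or non-imputed start date", so an imputed start is enough to trigger it, and "then the imputed stop date will be equal to the start date".

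Protocol 6.3.1 and SAP 7.1 collect medicines being received from Screening to Follow-up. Protocol 8.3.1 also records prior and current medications in the Screening history. Protocol 4.1.1 places Screening 10 to 28 days before the Treatment Period.

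**The concern.** Classing a medicine as concomitant when its dates are uncertain is a sensible, cautious convention. The difficulty is a record that is not uncertain on the point that matters. If the recorded stop month lies wholly before the first-dose month, every possible stop day is before Day 1, and so is every possible start day. The rules still assign a Day 1 start, then overwrite the recorded stop month so that it agrees with the imputed start.

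Such a medicine is missing from the prior table and wrongly present in the concomitant table. A related, smaller loss affects a medicine that was already in use before Day 1 and continues: its concomitant label is right, but a year-only start becomes Day 1 and removes it from the prior count.

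At stake is the accuracy of two descriptive tables for the Safety population.

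**Working it through.** The plan states no figure on this point, so the check is to apply the rules as written. The calendar dates are assumed for illustration: first dose 15 Sep 2021, last dose 28 days later on 13 Oct 2021.

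**Worked cases**

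| Recorded start | Recorded stop | Imputed start | Imputed stop | SAP 7.1 class | Agrees with record? |
|---|---|---|---|---|---|
| 2021 | Aug 2021 | 15 Sep 2021 | 31 Aug, reset to 15 Sep 2021 | concomitant only | no, both labels wrong |
| 2021 | Mar 2021 | 15 Sep 2021 | 31 Mar, reset to 15 Sep 2021 | concomitant only | no, both labels wrong |
| 2021 | 20 Aug 2021 | 20 Aug 2021 | 20 Aug 2021 | prior only | yes |
| 2020 | Aug 2021 | 31 Dec 2020 | 31 Aug 2021 | prior only | yes |
| Mar 2021 | Aug 2021 | 31 Mar 2021 | 31 Aug 2021 | prior only | yes |
| 2021, in use before Day 1 | ongoing | 15 Sep 2021 | ongoing | concomitant only | concomitant right, prior lost |

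Rows 1 and 3 isolate the cause. The only difference is whether the stop day is recorded, and the month alone already settles that the stop was before dosing.

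**Is the example special?** Take each first-dose day of a 365-day year and each earlier calendar month of that year as the stop month. The number of combinations is the sum over months of (days in month) × (month number − 1):

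28×1 + 31×2 + 30×3 + 31×4 + 30×5 + 31×6 + 31×7 + 30×8 + 31×9 + 30×10 + 31×11 = 2,017.

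With a year-only start, all 2,017 end with start = stop = Day 1: concomitant and not prior. The largest forward shift of the stop is from 31 Jan to 31 Dec, 334 days. With a complete earlier stop date there are 365×364/2 = 66,430 date pairs, and all 66,430 stay prior.

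**How often does the recorded month contradict the result?** Assume a year-only start, a month-only stop, first-dose dates spread evenly over the year, and a true stop 1 to 28 days before first dose in the same calendar year.

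- Cases: for the first 28 days of the year, 0+1+…+27 = 378; for the other 337 days, 337×28 = 9,436; total 9,814.
- Stop month before first-dose month: 28+27+…+1 = 406 per month, for 11 months, gives 4,466.
- Share: 4,466/9,814 = 45.5%.

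In the other 54.5% the stop month is the first-dose month. The record leaves the order open, and the concomitant class is defensible. The 45.5% is conditional on this pattern of partial dates and is not a prevalence.

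**The case against.** **The pattern should be uncommon.** In the example, Screening falls between 18 Aug and 5 Sep. If it is in September, a medicine ended in August was not being received at Screening and enters only through the history in Protocol 8.3.1. If it is in August, a medicine in use then and stopped by month end stopped while the daily diary (Protocol 8.4) was running, so a month-only stop is less likely. This stands as a limit on frequency. It does not make the rule right for the records that do occur.

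**The continuing medicine is correctly concomitant.** This also stands. Only its prior count is affected. SAP 7.1 tabulates participants by medicine and class, not by start date, so no planned summary table displays a Day 1 start.

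Three stronger readings are tempting, and the documents do not support them.

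- *A long-standing therapy would appear to breach Inclusion 8.* That criterion (Protocol 5.1) concerns stable regimens before dosing and is applied when eligibility is assessed. Nothing says that imputed dates are used for it.
- *A prohibited medicine stopped before dosing would remove a participant from the PD Evaluable population.* One deviation category in SAP 5.2 is "Received disallowed concomitant medication that could meaningfully impact results", but deviations are identified by review before database lock, and no text feeds imputed dates into that review. SAP 4.3.3 further requires that the violation could affect the PD assessment. The listed prohibited medicines are barred from the Screening Visit (Protocol 5.2, Exclusion 17, and Appendix 1), so use between Screening and Day 1 is already disallowed whatever date is imputed. One participant out of about 12 would be 8%, but no route to that loss is shown.
- *All medicines with partial dates are misclassified.* The 2,017 of 2,017 result describes the rule for one pattern. Earlier start years, known earlier start months and complete stop dates are handled correctly.

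**Conclusion.** The point holds as a minor defect. As written, SAP 16.3.1 and 16.3.2 together class a medicine as concomitant and not prior when its start is known only to the first-dose year and its recorded stop month is wholly before the first-dose month. The record contradicts that result, and the SAP itself avoids it when the stop date is complete. A year-only start also drops a continuing medicine, already in use before Day 1, from the prior count.

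For each such record the size is one medicine missing from the prior table and, in the first case, also wrongly counted as concomitant. The documents do not give the number of such records, and it may be zero. The consequence stops at the descriptive prior and concomitant medication tables. The primary endpoints (adverse events, and dose reductions or discontinuations due to TEAEs) do not use these dates, and no effect on Inclusion 8 or the PD Evaluable population is shown. The conclusion rests only on the SAP wording. The calendar dates are illustrative.

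**What to change.** In SAP 16.3.1, extend the stop-date check to partial stop dates. Take the latest possible stop (the last day of the recorded month, or 31 December of the recorded year). If it is before the imputed start, set the start to that date, provided this does not contradict a recorded start month or year. Query such conflicts instead of imputing over them.

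In SAP 16.3.2, move an imputed stop up to the start only when the start date is complete.

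Where the eCRF data identify a medicine as in use at Screening, also cap its imputed start at the Screening Visit date. This is conditional because Protocol 6.3.1 lists reason, dates and dosage, and no such identifier.

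In the first worked case the start and stop both become 31 Aug 2021, and the medicine is prior only. Truly uncertain dates, such as a stop in the first-dose month, stay concomitant as now.

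The cost is a few sentences in the SAP and a few lines of programming before database lock. The first two changes need no new data. The Screening cap depends on what the eCRF holds.

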16.3.2. Incomplete Stop Date

The following rules will be applied to impute the missing numerical fields. If the date of the last dose of double-blind study drug is missing, replace it with the last diary call date. If the imputed stop date is before the start date (imputed or non-imputed start date), then the imputed stop date will be equal to the start date.

Missing day and month

- If the year of the incomplete stop date is prior to the year of the date of the last dose of double-blind study drug, then December 31 will be assigned to the missing fields.

Missing month only

- The day will be treated as missing and both month and day will be replaced according to the above procedure.

Missing day only

- If either the year is before the year of the date of the last dose of double-blind study drug or if both years are the same but the month is before the month of the date of the last dose of double-blind study drug, then the last day of the month will be assigned to the missing day.
